#### 4) Findings Related to Possible Infection

- a. Evidence of active or latent tuberculosis (TB) as follows:
  - i. History of active TB, regardless of completion of adequate treatment
  - ii. Current signs or symptoms of active TB during screening as judged by the investigator
  - iii. Documentation of a chest x-ray obtained during screening (or results of an X-ray or computed tomographic [CT] scan of the chest within 6 months before screening) with evidence of current active or old active pulmonary TB
  - iv. Latent TB infection (LTBI), defined as a positive IFN-gamma release assay (IGRA) by QuantiFERON®-TB Gold, QuantiFERON®-TB Gold Plus, or T-Spot® testing at screening, or other diagnostic test, in the absence of clinical manifestations; **Note:** such subjects may be eligible if (1) there are no current signs or symptoms of active TB and (2) the subject has received adequate documented treatment for LTBI within 5 years of screening OR has initiated prophylactic treatment for LTBI per local guidelines and is rescreened now after 1 month of treatment. The subject must agree to complete a locally recommended course of treatment for LTBI to continue in the study
  - v. N/A per Revised Protocol 10
  - vi. An indeterminate IGRA result at screening with no signs or symptoms of active TB; **Note:** A subject with an indeterminate IGRA test result at screening must be retested for confirmation. If approved by the [REDACTED] medical monitor, the repeat test may be performed locally and may be a different type of IGRA assay. If the second result is again indeterminate, the TB questionnaire ([APPENDIX 20](#)) will be completed. If the TB questionnaire indicates no new/recent risks, then the subject may be eligible provided no other exclusion criterion for TB is met and ongoing IGRA testing will occur every 6 months per [Section 8.7.2](#). If there are new/recent risks, the subject will be excluded from the study. If the second result is positive, the subject should be treated as having LTBI. If the second result is negative, the subject may be eligible provided no other exclusion criterion for TB is met.
- b. Any of the following hepatitis B (HBV), hepatitis C virus (HCV), or human immunodeficiency virus (HIV) serology results at screening:
  - i. Evidence of HBV, defined as any of the following:
    - i. Positive hepatitis B surface antigen (HBsAg)
    - ii. Presence of HBV deoxyribonucleic acid (DNA)
    - iii. Positive for anti-hepatitis B core antibody (anti-HBc) without concurrent positive hepatitis B surface antibody (anti-HBs)

- ii. Evidence of HCV, defined as both of the following:
  - i. positive for antibodies to HCV
  - ii. positive result for confirmatory test for HCV (polymerase chain reaction)
- iii. Positive for antibodies to HIV-1 or HIV-2
- c. Currently receiving therapy for chronic infection (eg, pneumocystis, cytomegalovirus, herpes simplex, herpes zoster, invasive bacterial or fungal infections, or atypical mycobacteria); medications used for prophylaxis are not exclusionary
- d. History of congenital or acquired immunodeficiency
- e. Known active infection, or any major episode of infection requiring hospitalization or treatment with parenteral (intramuscular or IV) antimicrobial agents (eg, antibiotics, antiviral, antifungal, or antiparasitic agents) within 30 days before randomization, or completion of oral antimicrobial agents within 2 weeks before randomization
- f. Administration of a live vaccine or inactivated vaccine within 30 days before screening; influenza and pneumococcal vaccines may be administered at any time but the effect of BMS-986165 on vaccine response is unknown; live vaccines should not be used during treatment or within the 2 months following the last dose of blinded study treatment, and any other inactivated vaccines (eg, tetanus) should be used according to local guidelines during the treatment period
- g. Severe Acute Respiratory Syndrome Coronavirus 2 (SARS-CoV-2) infection (either suspected or confirmed) within 12 weeks of screening.

## 5) Physical Examination and Laboratory Results

- a. Evidence of organ dysfunction or any clinically significant deviation from normal in physical examination, vital signs, or clinical laboratory determination beyond what is consistent with the target population
- b. Clinically significant abnormalities on screening chest x-ray or electrocardiogram (ECG) unless due to SLE
- c. Clinically significant abnormalities in screening laboratory results, including:
  - i. Positive direct antiglobulin test (Coombs test) and evidence of hemolysis
  - ii. Serum alanine aminotransferase (ALT)  $> 2 \times$  upper limit of normal (ULN), unless explicitly related to SLE
  - iii. Serum aspartate aminotransferase (AST)  $> 2 \times$  ULN, unless explicitly related to SLE
  - iv. Serum total bilirubin  $> 1.5 \times$  ULN, unless explicitly related to SLE or documented Gilbert's syndrome
  - v. Hemoglobin  $< 8$  g/dL (80 g/L)
  - vi. eGFR (using the MDRD equation)  $\leq 30$  mL/min/1.73 m^2
  - vii. Absolute neutrophil count (ANC)  $< 1.2 \times 10^3/\mu\text{L}$  ( $1.2 \times 10^9/\text{L}$ )
  - viii. Platelet count  $< 50 \times 10^3/\mu\text{L}$  ( $50 \times 10^9/\text{L}$ )

- d. Abnormal free T4: if a subject has an abnormal TSH at screening (relative to the laboratory reference range), free T4 will be assessed. Those with abnormal free T4 will be excluded unless they have a prior diagnosis of a thyroid disorder and are currently receiving thyroid replacement therapy; these subjects may rescreen after a minimum of 6 weeks after adjustment of thyroid hormone replacement therapy. Such cases should be discussed with the [REDACTED] medical monitor. Any other significant laboratory or other abnormalities that, in the opinion of the investigator, might pose an unacceptable risk to the subject during the study

## 6) Allergies and Adverse Drug Reaction

- a. History of any significant drug allergy (such as anaphylaxis or hepatotoxicity)

## 7) Other Exclusion Criteria

- a. Involuntary incarceration such as imprisonment (Note: under certain specific circumstances a person who has been imprisoned may be included or permitted to continue as a subject. Strict conditions apply and BMS approval is required)
- b. Compulsory detention for treatment of psychiatric or physical illness (eg, infectious disease)
- c. Inability to comply with the study protocol

## 5.3 Lifestyle Restrictions

No restrictions are required. However, general skin care measures are recommended that are standard for patients with SLE, as follows: use of broad spectrum sunscreen (minimum sun protection factor 15 and with inorganic ingredients [zinc oxide, titanium dioxide]), avoiding sun exposure, wearing sun-protective clothing, avoiding alcohol-based emollients, over-the-counter anti-acne medications, alcohol-based skin care products, and perfumed soaps and detergents, and similar measures.

### 5.3.1 Meals and Dietary Restrictions

The blinded study treatment may be taken without regard to meals; however, subjects are required to fast for a minimum of 10 hours before visits at which blood samples will be collected for the fasting lipid profiles [REDACTED].

### 5.3.2 Caffeine, Alcohol, and Tobacco

There are no study-specific restrictions on caffeine, alcohol, or tobacco use.

### 5.3.3 Activity

There are no restrictions on physical activity.

## 5.4 Screen Failures

Screen failures are defined as subjects who consent to participate in the clinical study but who do not meet the study eligibility criteria. A minimal set of screen failure information is required to ensure transparent reporting of screen failure subjects, to meet the Consolidated Standards of Reporting Trials (CONSORT) publishing requirements, and to respond to queries from regulatory

authorities. Minimal information includes date of consent, demographic data, screen failure details, eligibility criteria, and any serious AEs (SAEs).

#### **5.4.1 Retesting During the Screening Period**

The study permits the re-enrollment of a subject who discontinues the study as a pretreatment failure (ie, the subject fails screening and has not been treated), with the approval of the [REDACTED] medical monitor. If re-enrolled, the subject must sign a new informed consent form (ICF). In some instances, investigators may rescreen a subject more than once after discussion with and approval of the medical monitor.

Laboratory parameters and/or assessments that are included in [Table 1](#) may be repeated one time in an effort to find all possible well-qualified subjects. Consultation with the [REDACTED] medical monitor may be needed to identify whether repeat testing of any particular parameter is clinically relevant.

The most current result will be used to assess eligibility for study inclusion because it represents the subject's most current clinical state.

If a subject is rescreened, the same parameters regarding the time since renal biopsy and chest x-ray, and time on MMF therapy will apply.

## **6 TREATMENT**

Study treatment is defined as any investigational treatment, marketed product, placebo, or medical device intended to be administered to a study subject according to the study randomization or treatment allocation.

An IP, also known as investigational medicinal product in some regions, is defined as a pharmaceutical form of an active substance or placebo being tested or used as a reference in a clinical study, including products already with a marketing authorization but used or assembled (formulated or packaged) differently than the authorized form, or used for an unauthorized indication, or when used to gain further information about the authorized form.

Other medications used as support or escape medication for preventive, diagnostic, or therapeutic reasons, as components of the standard of care for a given diagnosis, may be considered to be non-IPs. [Table 5](#) shows the treatments for this study.

**Table 5: Study Treatments for Protocol IM011073**

Product Description/ Class and Dosage Form	Potency	IP/Non-IP	Blinded or Open Label	Packaging/ Appearance	Storage Conditions (per label)
BMS-986165 oral tablet	3 mg or 6 mg	IP	Blinded	Blister card containing 64 tablets	Store at 15° to 25°C. Store in original container. Protect from light.
Placebo matching BMS-986165 oral tablet	N/A	IP	Blinded	Blister card containing 64 placebo tablets	Store at 15° to 25°C. Store in original container. Protect from light.
Mycophenolate mofetil	500 mg	IP	Open label	Bottles or blister card of tablets	See storage conditions on the container

IP = investigational product

### 6.1 Mycophenolate Mofetil Target Dose and Dose Modification

For subjects who will be starting MMF in Part A, treatment will be initiated at 500 mg BID. If tolerated, the dose will be increased to a suggested target dose of 1.5 to 2.0 g/day (subjects self-described as Asian) or 2.0 g/day (all others) one week after initiating MMF. Subjects who have been on MMF at a dose of  $\leq 750$  mg/day at the time of screening will follow the same escalation schedule as those starting MMF. For subjects self-described as Black, African American, or of African descent, the dose will be further increased to 3.0 g/day two weeks after initiating MMF. The following suggested target doses of MMF should be reached by the time of randomization:

- 1.5 to 2.0 g/day for subjects self-described as Asian or of Asian descent
- 3.0 g/day for subjects self-described as Black, African American, or of African descent
- 2.0 g/day for all others, with the following exception:

Subjects entering the study on a stable dose of MMF greater than the target may continue that dose if it is no greater than 3.0 g/day. In some non-African subjects, the investigator may believe that it is in the best interest of the subject to use doses higher than 2.0 g/day; this is allowed provided the dose is not higher than the maximum of 3.0 g/day.

From Week 6 of MMF treatment in Part A through the end of Part B, the MMF dose should remain stable with the following exceptions:

- A change from a BID to a three times daily (TID) regimen is permitted as long as the total daily dose remains unchanged
- Per the MMF prescribing information, if neutropenia develops ( $ANC < 1300/\mu L$ ), MMF dosing should be interrupted or the dose reduced, appropriate diagnostic tests should be performed, and the subject should be managed appropriately.

After a subject reaches the target dose, the dose should remain stable through the end of Part B; however, if necessary because of intolerance, the rate of dose increase may be slowed, or the dose may be divided and administered TID, at the discretion of the investigator.

If a subject cannot tolerate the MMF dose or the investigator has concerns about over-immunosuppression, the target dose may be reduced; however, subjects unable to tolerate a minimum dose of 1.5 g/day in Part A should be discontinued from study treatment and will be considered enrollment failures.

Women of childbearing potential who are starting MMF in Part A must have a negative urine pregnancy test within 24 hours before the first dose, and per the MMF prescribing information, these subjects should also have another urine pregnancy test between 8 and 10 days after the first dose. For the subjects' convenience, this second pregnancy test may be performed at a local laboratory; the site staff should call subjects to whom this requirement applies and remind them to obtain the test at the investigative site or a local laboratory.

## **6.2 Laboratory Monitoring for Mycophenolate Mofetil Toxicity**

In accordance with the prescribing information, subjects should have a complete blood count (CBC) performed weekly for the first month of MMF therapy, twice monthly for the second and third month, and then monthly thereafter for the first year of therapy. If these monitoring CBCs coincide with scheduled study visits, the central laboratory results for that visit may be used; if any of these CBCs are needed in between scheduled study visits, these may be performed at a local laboratory. The site staff should contact subjects to whom this monitoring applies and remind them to obtain the test either at the investigative site or a local laboratory.

For those subjects already taking MMF before signing the ICF, it is expected that the investigator will manage safety monitoring per the standard of care and in accordance with the MMF prescribing information.

## **6.3 Treatments Administered**

### **6.3.1 Open-label Mycophenolate Mofetil – All Subjects**

Open-label MMF will be dispensed to all subjects in Part A, Part B [REDACTED].

### **6.3.2 Blinded Study Treatment in Part B – Randomized Subjects Only**

[figure not shown]
Blinded study treatment in Part B will be supplied in blister card kits. The tablets will be arranged into sets to be taken in the morning and in the evening, approximately 12 hours apart. If a subject forgets a dose of blinded study treatment, but remembers within 4 hours of the expected dose, the dose should be taken. If the missed dose is discovered more than 4 hours after it should have been taken, that dose should be not be taken and the next scheduled dose should be taken at the usual time. Any missed doses should be returned at the next study visit.

Table 6 shows the blinded study treatments in Part B.

**Table 6: Selection and Timing of Blinded Study Treatment Dosing**

Treatment Group	Unit dose strength	Dosage formulation Frequency of Administration	Route of Administration
3 mg BID BMS-986165	3 mg	1 active and 1 placebo tablet in the morning and 1 active and 1 placebo tablet in the evening	Oral
6 mg BID BMS-986165	6 mg	1 active and 1 placebo tablet in the morning and 1 active and 1 placebo tablet in the evening	Oral
Placebo BID	N/A	2 placebo tablets in the morning and 2 placebo tablets in the evening	Oral

BID = twice daily

#### **6.4 Subject Number Assignment**

At the screening visit, before any study-related procedures are performed, the investigative site will access the interactive response technology (IRT) for assignment of the subject number. This number will be assigned sequentially by the system and will be unique across all sites. If a potential subject is rescreened, they will be given a new identification number.

#### **6.5 Blinding – Part B**

At Visit B1, subjects who meet the criteria to continue in Part B and meet the randomization criteria will be centrally randomized using IRT to receive BMS-986165 3 mg BID, BMS-986165 6 mg BID, or placebo BID. These criteria are listed in [Section 4.1.2.1](#) and [4.1.2.2](#), respectively.

[REDACTED]

All blinded study treatments will be supplied in blister packs with each daily dose made up of active or placebo tablets. The investigative site staff, Sponsor and designated personnel, and subjects and their families will remain blinded to treatment assignments through the end of Part B.

This study will be conducted as a double-blind study for the placebo-controlled treatment period (Part B). [REDACTED]

For the Week 24 database lock (primary efficacy endpoint), personnel who have access to the unblinded data are not to discuss or make materials available that would unblind individual subjects' data to the personnel involved in the study conduct. Access to treatment codes will be restricted from all participants and site personnel prior to final database lock, with exceptions as specified below.

Blinding of randomized treatment assignment is critical to the integrity of this clinical study. However, in the event of a medical emergency or pregnancy in an individual subject in which knowledge of the blinded study treatment is critical to the subject's management, the blind for that subject may be broken by the investigator. The subject's safety takes priority over any other considerations in determining if a treatment assignment should be unblinded. In case of an emergency, the investigator has unrestricted access to randomization information and may break the blind through the IRT system without prior approval from the Sponsor. Following the unblinding, the investigator shall notify the [REDACTED] medical monitor.

Before breaking the blind of an individual subject's treatment, the investigator should determine that the unblinded information is necessary, ie, that it will alter the subject's immediate management. In many cases, particularly when the emergency is clearly not related to the blinded study treatment, the problem may be properly managed by assuming that the subject is receiving active product. It is highly desirable that the decision to unblind treatment assignment be discussed with the [REDACTED] medical monitor, but the investigator always has ultimate authority for the decision to unblind. The Principal Investigator should call in for emergency unblinding only after the decision to discontinue the subject has been made.

In cases of accidental unblinding, the investigator must contact the [REDACTED] medical monitor and ensure every attempt is made to preserve the blind.

Any request to unblind a subject for nonemergency purposes should be discussed with the [REDACTED] medical monitor.

## 6.6 Dosage Modification

There is no provision for modification of the dose of blinded study treatment.

Corticosteroid tapering is discussed in Section 6.6.1.

See [Section 6.1](#) for information about MMF dose modification.

### 6.6.1 **Corticosteroid Tapering and Corticosteroid Rescue in Part B**

Corticosteroids are permitted but not required in this study. One of the criteria to continue in the study during Part B is that the corticosteroid dose (if any) must not exceed 25 mg/day of prednisone or prednisone equivalent. Management of corticosteroids including initiation and dosing in Part A will be at the discretion of the investigator. All corticosteroid doses in this section of the protocol refer to prednisone. See [APPENDIX 6](#) for prednisone-equivalent doses of other corticosteroids.

For subjects deemed by the investigator to be appropriate for corticosteroid tapering, this section includes a guideline and a suggested sequence of tapering.

Subjects will be assessed for SLE flare at study visits every 4 weeks throughout Part B. Flare assessments will be made in comparison to the previous visit. Corticosteroid doses may be tapered at the time of a study visit, and at the investigator's discretion, subjects may be instructed to adjust the corticosteroid dose in between study visits. For example, at a study visit, an investigator may taper the dose and instruct a subject to taper again to the next lower dose (to be specified) 2 weeks later if they are feeling well. Likewise, after a study visit at which the dose is tapered, an investigator may instruct the subject to resume the previous dose before the next study visit if needed because of intolerance.

Subjects who respond to MMF during Part A and therefore do not meet the randomization criteria, but who continue open-label MMF in Part B will follow the same corticosteroid taper.

Randomized subjects taking corticosteroids will be required to have their dose tapered during Part B unless there is evidence of increased extrarenal disease activity as assessed by the rSFI (clinical component only; the renal system will not be assessed with the rSFI; see [APPENDIX 17](#)) or worsening or unstable renal findings per the OSS Flare Index (see [APPENDIX 16](#)) as follows:

- If either flare index indicates a moderate or severe flare, the corticosteroid dose should not be tapered
- If either flare index indicates a mild flare, or if there is no flare but there is another reason not to taper the corticosteroid dose, the investigator must contact CRS, which will refer the case to the study-designated nephrology or rheumatology Therapeutic Expert for additional review

Unless they have a moderate or severe flare as defined above, randomized subjects will have their corticosteroid dose tapered as follows:

- Corticosteroid dose tapering should start by Week 4 in Part B

- After the dose is tapered to the lower dose level, subjects should remain on the new corticosteroid dose for at least 2 weeks before further tapering
- The goal for corticosteroid tapering is to reduce the dose to 7.5 mg/day prednisone or equivalent by Week 24; the dose may continue to be tapered below 7.5 mg/day at the investigator's discretion
- Subjects on a baseline dose of 25 mg/day of prednisone or equivalent will have their dose tapered by 5 mg to 20 mg/day; thereafter, the dose will be tapered by 2.5-mg increments until they reach 7.5 mg/day (tapering may continue at the discretion of the investigator)
- Subjects on a baseline dose of  $\leq 20$  mg/day of prednisone or equivalent will have their dose tapered by 2.5-mg increments until they reach 7.5 mg/day (tapering may continue at the discretion of the investigator)
- No dose tapering will occur during the 4 weeks leading up to the visit at Week 24 and at Week 52, to allow 4 weeks of stable dosing before the efficacy assessments at these visits; in other words, the dose may be tapered at Week 20, but then should remain stable until the efficacy assessments at Week 24; similarly, the dose may be tapered at Week 48, but then should remain stable until the efficacy assessments at Week 52
- During the course of corticosteroid dose tapering, resumption of the previous dose (one dose level higher than the current dose) is allowed, but resumption of a dose higher than the previous dose (more than one dose level higher than the current dose) is not allowed, except for the following:
  - During the first 8 weeks in Part B, a single corticosteroid burst of up to 40 mg/day prednisone or equivalent is allowed, but the dose must be tapered back to the previous dose within 2 weeks after initiating the burst
- [REDACTED]

In the following situations, subjects may continue to receive blinded study treatment in Part B but will be considered nonresponders for analysis purposes:

- The corticosteroid burst dose cannot subsequently be tapered within 2 weeks of initiating the burst
- More than a single corticosteroid burst is needed
- A corticosteroid burst is needed after Week 8
- There is a need to increase the dose by more than one dose level higher than the current dose

Table 8 shows the recommended sequence of corticosteroid dose reductions that should be followed for all subjects, according to the dose at the time of randomization, but the actual frequency of tapering and duration of time at each tapered dose may vary between subjects and will be determined by the investigator.

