### **4.4 Scientific Rationale for Study Design**

#### **4.4.1 Rationale for Overall Study Design**

The objectives of this study are to evaluate the efficacy and safety of BMS-986165 in subjects with ISN/RPS Class III or IV (alone or in combination with Class V) LN. A placebo control is included to allow the effects of treatment both desired and adverse, to be appropriately attributed to treatments received. The use of a placebo group is balanced by the fact that all subjects will continue concomitant background treatment with MMF, with or without corticosteroids, which are standard-of-care treatments for patients with LN.

The eligibility criteria have been designed to minimize the risk for serious infections that may be associated with immunosuppressive therapies.

The protocol includes a plan for corticosteroid tapering at regular intervals during Part B to assess whether the effects of BMS-986165 on renal function allow for reduction of the corticosteroid

dose and associated complications. The protocol has a provision for a single corticosteroid rescue, provided the dose can then be tapered down within 2 weeks.

Safety and efficacy results will be assessed throughout the study to allow timely management of any concerns that arise. Subjects will attend study visits every 4 weeks [REDACTED] and will be closely monitored for AEs. A DMC will monitor safety and efficacy findings throughout the study to allow timely management of any concerns that could arise. Use of the Revised Safety of Estrogens in Lupus Erythematosus National Assessment (SELENA) Flare Index (rSFI) and Ohio SLE Study (OSS) Flare Index in addition to frequent clinical and laboratory assessments will allow prompt detection of disease flare so subjects can be properly managed with regard to their disease, and to accurately assess the renal response.

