**Table 8: Corticosteroid Dose Tapering Sequence by Dose at Randomization (Visit B1)**

Sequence	Prednisone or Equivalent Dose (mg/day) at Randomization								
	25	20	17.5	15	12.5	10	7.5	5	2.5
Taper 1	20	17.5	15	12.5	10	7.5	5	2.5	0
Taper 2	17.5	15	12.5	10	7.5	5	2.5	0	
Taper 3	15	12.5	10	7.5	5	2.5	0		
Taper 4	12.5	10	7.5	5	2.5	0			
Taper 5	10	7.5	5	2.5	0				
Taper 6	7.5	5	2.5	0					
Taper 7	5	2.5	0						
Taper 8	2.5	0							
Taper 9	0								

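### Does the fourth nonresponder rule in Section 6.6.1 penalise the permitted corticosteroid burst, and leave the primary analysis undefined after such events?

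*Combined protocol and SAP*

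**What the plan says.** Section 6.6.1 of the protocol sets a conduct rule for subjects whose corticosteroid dose is being tapered: "resumption of a dose higher than the previous dose (more than one dose level higher than the current dose) is not allowed". One exception is attached. During the first 8 weeks of Part B, "a single corticosteroid burst of up to 40 mg/day prednisone or equivalent is allowed", with return to the previous dose within 2 weeks. Section 4.4.1 gives the design intent: "The protocol has a provision for a single corticosteroid rescue, provided the dose can then be tapered down within 2 weeks".

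After a blacked-out bullet, Section 6.6.1 lists four situations in which "subjects may continue to receive blinded study treatment in Part B but will be considered nonresponders for analysis purposes":

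1. A burst that cannot be tapered within 2 weeks.
2. More than one burst.
3. "A corticosteroid burst is needed after Week 8".
4. "There is a need to increase the dose by more than one dose level higher than the current dose".

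The primary endpoint (Section 9.3.1) is the percentage change in 24-hour UPCR at Week 24. Section 9.4.1.1 imputes missing Week 24 values. It also sets to missing any assessment made after a prohibited treatment that could improve lupus nephritis. The prohibited list in Section 6.10.1 leaves out corticosteroids (item 5) and rescue with prednisone or equivalent (item 9). Section 9.4.2.1 imputes nonresponse for the binary endpoints after early discontinuation, prohibited treatment or missing data, up to the endpoint visit. It does not refer to Section 6.6.1.

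**The concern.** There are two apparent defects.

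**Classification.** The exception for the burst belongs to the conduct rule and is not repeated in the nonresponder list. A subject with one fully compliant burst could be programmed either as a possible responder or as an automatic nonresponder for partial and complete renal response.

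**Primary analysis.** Partial renal response at Week 24 and the primary endpoint use the same 24-hour UPCR. After a listed event the first is nonresponse, while the second has no stated rule, because nonresponder has no value on a percentage change. Part of a UPCR fall could be due to the extra steroid and still count for the arm. The plan itself treats steroid exposure as relevant. It stratifies on recent IV dose, and it freezes tapering before Weeks 24 and 52 "to allow 4 weeks of stable dosing before the efficacy assessments at these visits".

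**Working it through.** **1. Does the overlap exist?** The Table 8 levels are 0, 2.5, 5, 7.5, 10, 12.5, 15, 17.5, 20 and 25 mg/day. The largest step between neighbours is 25 − 20 = 5 mg. A burst to 40 mg/day lies 40 − 25 = 15 mg to 40 − 0 = 40 mg above the listed doses, so it exceeds one level from each of them. Smaller bursts can do so as well: from 7.5 mg/day one level up is 10, so 12.5 already meets situation 4. A rise of exactly one level needs no exception, since return to the previous dose is allowed anyway. The literal overlap is therefore real and covers essentially every burst for which the exception is needed.

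**2. Which reading fits the text?**

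| Reading of situation 4 | Situations 1 to 3 | Exception clause and Section 4.4.1 |
|---|---|---|
| Includes the compliant burst | Largely redundant: a burst that breaks the 2-week, single-use or Week 8 limit already meets situation 4 | A subject using the stated provision is always a nonresponder |
| Excludes the compliant burst | Each limit has its own consequence | Consistent |

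Situations 1 to 3 speak of bursts. Situation 4 speaks of dose increases and echoes the conduct rule, whose only visible exception is the burst. The second reading is the only one under which all four situations have a purpose.

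**3. Size if the literal reading were applied.** One relabelled subject changes the placebo rate by 1/26 = 3.8 points or the combined active rate by 1/52 = 1.9 points. As an assumed illustration, take 21/52 against 6/26 responders: 40.4% − 23.1% = 17.3 points.

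- Relabel 3 active responders: 18/52 − 6/26 = 11.5 points.
- Relabel 3 placebo responders: 21/52 − 3/26 = 28.8 points.
- Relabel 6 active and 3 placebo (equal shares of the arms): 15/52 − 3/26 = 17.3 points.

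**4. Primary analysis.** Section 9.4.1.1 removes a value only if it follows a prohibited treatment. Section 6.10.1 does not prohibit corticosteroids or prednisone-equivalent rescue. An observed Week 24 UPCR therefore stays in as measured. A compliant burst starts by Week 8 and is tapered back by Week 8 + 2 = Week 10 at the latest, which is 24 − 10 = 14 weeks before the assessment and well beyond the 4-week stability period.

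**5. Would setting such values to missing be better?** The 88% power in Section 9.1 cannot be reproduced, because the visible text gives no effect size or SD. Solving backwards (52 against 26, one-sided 0.10, noncentral t) gives an effect of 0.593 SD.

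Assume that 6/26 placebo and 6/52 active subjects escalate, that escalation lowers UPCR by 30% to 50%, and that the log-scale SD is 0.7 to 1.0.

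- Shift against the drug: (6/26 − 6/52) × ln(1/0.7) = 0.041, or × ln 2 = 0.080.
- Standard error: SD × √(1/26 + 1/52) = 0.168 to 0.240. The shift is then 0.17 to 0.48 standard errors.
- Power as observed: 84% to 76%.
- Power with those subjects missing (46 against 20): 82.1%.

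The second figure lies inside the first range, so neither handling is uniformly better. If equal shares escalate, the shifts cancel and as-observed power stays near 88%. Setting 6/52 and 3/26 to missing (46 against 23) then gives 84.8%.

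**The case for a change.** The strongest case for a change is that a rule which assigns endpoint status has to be programmed and should not depend on inference. Section 9.4.2.1 could have settled it and does not mention Section 6.6.1. Section 6.6.1 also describes larger increases as not allowed, so a programmer could class a breach as prohibited treatment and set the Week 24 UPCR to missing. The choice should be fixed before the Week 24 database lock (Section 9.6.5), when unblinded analyses begin, and the wording would cost little.

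What stands is that the visible text does not state either answer in one place. That is missing detail. Section 9.4 leaves full analysis detail to the SAP, to be finalised before database lock. The blacked-out bullet sits directly between the burst exception and the nonresponder list. Either may already hold the answer.

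Two further arguments do not hold:

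- **Raised false-positive rate if the active arms use more steroid.** If the drug affects nothing, randomization makes expected steroid use equal and the test keeps its level. If the drug does change steroid use, the as-observed effect is not null.
- **Comparison with the 250 mg stratum.** A burst of 40 × 14 = 560 mg prednisone converts by Appendix 6 to 560 × 16/20 = 448 mg methylprednisolone. But that sets a permitted early oral course, at its upper bound, against IV dosing before randomization.

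Treating an event as failure in a binary endpoint while keeping the observed value in a continuous one is a common and legitimate difference of approach.

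**Conclusion.** No change follows. The literal overlap between situation 4 and the permitted burst is a drafting slip that the rest of Section 6.6.1 and Section 4.4.1 resolve. On the resolved reading a compliant burst changes no one's responder status. The primary analysis has a workable default, use as observed, that follows from Sections 6.10.1 and 9.4.1.1, and the alternative offers no clear gain. For the time limit, analysts can sensibly use the at-or-before-endpoint anchor already in Section 9.4.2.1.

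The 1.9 or 3.8 points per subject would matter only under the literal reading. The documents give no expected rate of bursts or escalations, so the response-rate and power figures are illustrations on assumed inputs. The conclusion rests on the visible wording and assumes that neither the blacked-out bullet nor the SAP says the opposite. It takes no view on the corticosteroid rules themselves.
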